**Student Investigator/Intern:**

**Collaborating Institute(s):**

**Population: Inclusion of special groups (Check all that apply):**

- |   |  |
|---|--|
| Gender                               |  Pregnant Women                                      |
|  Male    |  Fetuses   |
|  Females |  Prisoners   |
| Age                                  |  Destitutes  |
|  0 – 5 years        |  Service providers                                   |
|  5 – 9 years        |  Cognitively Impaired                                |
|  10 – 19 years      |  CSW   |
|  20 +               |  Others (specify: 6 – 15 years age group) |
|  > 65               |  Animal  |

**Project / study Site (Check all the apply):**

- |  |  |
|--|--|
|  Dhaka Hospital      |  Mirsarai             |
|  Matlab Hospital     |  Patyia                          |
|  Matlab DSS area     |  Other areas in Bangladesh _____ |
|  Matlab non-DSS area |  Outside Bangladesh _____        |
|  Mirzapur            | name of country: _____                                   |
|  Dhaka Community     |  Multi centre trial              |
|  Chakaria            | (Name other countries involved)                          |
|  Abhoynagar          | _____  |

**Type of Study (Check all that apply):**

- |  |   |
|--|---|
|  Case Control study                              |  Cross sectional survey                   |
|  Community based trial / intervention |  Longitudinal Study (cohort or follow-up) |
|  Program Project (Umbrella)                      |  Record Review                            |
|  Secondary Data Analysis                         |  Prophylactic trial                       |
|  Clinical Trial (Hospital/Clinic)                |  Surveillance / monitoring                |
|  Family follow-up study                          |  Others                                   |

**Targeted Population (Check all that apply):**

- |   |                                      |
|---|--------------------------------------|
|  No ethnic selection (Bangladeshi) |  Expatriates |
|  Bangalee                                     |  Immigrants  |
|  Tribal groups                                |  Refugee     |

**Consent Process (Check all that apply):**

- |   |  |
|---|--|
|  Written |  Bengali language |
|  Oral               |  English language |
|  None               |  |

**Proposed Sample size:**

Total sample size: 350

Sub-group

**Determination of Risk: Does the Research Involve (Check all that apply):**

- |   |  |
|---|--|
|  Human exposure to radioactive agents?          |  Human exposure to infectious agents?                          |
|  Fetal tissue or abortus?                       |  Investigational new drug                                      |
|  Investigational new device?
(specify _____) |  Existing data available via public archives/source |
|  Existing data available from Co-investigator   |  Pathological or diagnostic clinical specimen only             |
|   |  Observation of public behaviour                               |
|   |  New treatment regime  |

**Yes/No**

Is the information recorded in such a manner that subjects can be identified from information provided directly or through identifiers linked to the subjects?

Does the research deal with sensitive aspects of the subject's behaviour; sexual behaviour, alcohol use or illegal conduct such as drug use?

Could the information recorded about the individual if it became known outside of the research:

a. place the subject at risk of criminal or civil liability?

b. damage the subject's financial standing, reputation or employability; social rejection, lead to stigma, divorce etc.

**Do you consider this research (Check one):**

- |  |   |
|--|---|
|  greater than minimal risk |  no more than minimal risk |
|  no risk                   |  only part of the diagnostic test     |

Minimal Risk is "a risk where the probability and magnitude of harm or discomfort anticipated in the proposed research are not greater in and of themselves than those ordinarily encountered in daily life or during the performance of routine physical, psychological examinations or tests. For example, the risk of drawing a small amount of blood from a healthy individual for research purposes is no greater than the risk of doing so as a part of routine physical examination".

Yes/No

Is the proposal funded?

If yes, sponsor Name: \_\_\_\_\_

Yes/No

Is the proposal being submitted for funding ?

If yes, name of funding agency: (1) \_\_\_\_\_ MOST, USAID

(2) \_\_\_\_\_

Do any of the participating investigators and/or their immediate families have an equity relationship (e.g. stockholder) with the sponsor of the project or manufacturer and/or owner of the test product or device to be studied or serve as a consultant to any of the above?

*IF YES, submit a written statement of disclosure to the Director.*

**Dates of Proposed Period of Support**

(Day, Month, Year - DD/MM/YY)

Beginning date 01/11/2001

End date 31/10/2002

**Cost Required for the Budget Period (\$)**

a. Ist Year 2nd Year 3rd Year Other years

\$129,866 \_\_\_\_\_

b. Direct Cost : \$106,293 Total Cost : \$129,866

Fortification of an appropriate food is considered to be a cost-effective and sustainable strategy to address micronutrient malnutrition in deficient populations. In many parts of the world, wheat flour is fortified with minerals and vitamins with an aim to improve micronutrient status of a deficient population or maintain an already improved status. In Bangladesh, most of the population groups, and especially those who belong to the lower strata of the society are suffering from micronutrient deficiencies of varying degrees. Vitamin A and iron deficiencies have been identified as two major micronutrient deficiencies that have highly significant public health implications. In the long run, consumption of wheat flour fortified with vitamin A and iron by members of vulnerable families improves the growth and health of the children as well as micronutrient status of others who consume it. Instead of whole wheat or unfortified flour, using fortified wheat flour for feeding programs aiming at improving nutritional status of vulnerable groups seems logical. The purpose of this pilot study is to determine if any effect can be demonstrated, primarily in terms of improved vitamin A status; and also iron status among children consuming *Chapattis* made from flour fortified with vitamin A and iron. A positive impact will justify use of fortified flour in this part of the world.

We propose to conduct a randomized, double-blind controlled trial in a rural area of Chittagong district in Bangladesh. A total of 350 apparently healthy school aged children (6-15 years) will be enrolled from a randomly selected clusters of *baris* (each bari is composed of 5 –6 households having a total of 30 inmates) under the study area. The selected baris will be randomized to receive in a blinded manner either fortified or unfortified wheat flour according to a six-block scheme. Three of these blocks will contain fortified flour and the rest will be unfortified. A bari mother will be selected to prepare and serve the *chapattis* along with a condiment (i.e. Dal/Suji/Sugar) to the study subjects, and should also ensure their daily consumption. The children will consume *chapattis* made from 100g of wheat flour on a daily basis for a period of six months. An assigned house member will keep a written record of *chapatti* consumption. This will be followed by spot checks at least twice a month by field staff. The impact on vitamin A and iron

status will be assessed by determining changes in serum concentrations of retinol, ferritin, transferrin receptor (TfR) and hemoglobin before and after intervention in the treatment and control groups. These markers will be the outcome measures of any change in vitamin A and iron status in the children. A mid-point blood analysis at 3 months will also be done to measure of the onset of a detectable change.

Concerned agencies may use the results of this study for planning food fortification program in Bangladesh as well as in other developing countries. It may also stimulate local food companies to come forward with new strategies in areas of fortification and take an effective role in micronutrient intervention programs. Similarly, the Government of Bangladesh may use this information to formulate policies regarding food fortification.

KEY PERSONNEL (List names of all investigators including PI and their respective specialties)

Name	Professional Discipline/ Specialty	Role in the Project
1. I. [name]	Senior Operations Researcher / Nutrition	PI
2. [name]	Director, ICDDR,B	Co-PI
3. [name]	Senior Operations Researcher / Public Health Research	Co-PI
4. [name]	Operations researcher / Public Health research	Co-Investigator
5. [name]	Associate scientist / Biochemistry Lab	Co-Investigator
6. [name]	Scientist / Clinical nutrition	Co-Investigator
7. [name]	Field Operations Manager	Co-Investigator
8. [name]	Associate Scientist / Paediatric Nutrition	Co-Investigator

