### Specific Aims:

Describe the specific aims of the proposed study. State the specific parameters, biological functions/ rates/ processes that will be assessed by specific methods (TYPE WITHIN LIMITS).

The aim of the study is to evaluate whether an impact of consuming *chapatti* made from vitamin A and iron fortified wheat flour by the school aged children can be demonstrated

1. Primarily, on their vitamin A status reflected in serum retinol concentration at 6 months
2. Secondly, on iron status reflected in serum ferritin, TfR and hemoglobin concentration at 6 months

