#### SAMPLE SIZE ESTIMATION:

Sample size was estimated by taken into account the *mean and standard deviation (SD) of serum retinol concentrations*. Unfortunately, there are no data on serum retinol or serum ferritin distributions in this age group in rural Bangladesh on which to base a sample size. However, in a trial in Guatemala [Arroyave et al. 1981] (22), the mean  $\pm$  SD of serum retinol concentrations were  $29.2 \pm 10.2$   $\mu\text{g/dL}$  and  $34.2 \pm 9.5$   $\mu\text{g/dL}$  before and after 1 year of supplementation with sugar fortified with vitamin A. With this level of change, we require 83 subjects in each group (5% significance level and a power of 90%).

Sample size was also estimated by taken into account the *mean and standard deviation (SD) of serum ferritin concentrations*. In a trial in Venezuela [Layrisse et al. 1996] (14), the mean  $\pm$  SD of serum ferritin concentrations were  $18.01 \pm 13.8$   $\mu\text{g/L}$  and  $25.2 \pm 15.3$   $\mu\text{g/L}$  before and after supplementation with maize and wheat flour fortified with iron. With this level of change, we require 87 subjects in each group (power of 90% and 5% level of significance).

Considering the greater of the two estimates (87 subjects), the calculated sample size has been doubled to 175 in each group to account for cluster and dropout effects. With a population of 30 in each bari in the study area and 4 eligible children (6-15 years) in each bari we require 44 baris in the experimental and 44 baris in the control group.

Sample size estimation was done by using the formula:

$$\frac{2(\text{SD})^2 \times \text{factor for } \alpha, \beta}{(\text{WD})^2}$$

Where, SD is the standard deviation and WD is the worthwhile difference between the means.

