## Data Analysis

Describe plans for data analysis. Indicate whether data will be analyzed by the investigators themselves or by other professionals. Specify what statistical softwares packages will be used and if the study is blinded, when the code will be opened. For clinical trials, indicate if interim data analysis will be required to monitor further progress of the study. (TYPE WITHIN THE PROVIDED SPACE).

The groups will be compared to ensure the comparability of the groups at the start of the study. The comparisons will include z-scores of weight-for-age (WA), height-for-age (HA) and weight-for-height (WH), hemoglobin, serum retinol, serum ferritin and serum TfR. These should be statistically similar at the start of the study. However, randomization design of the study is also expected to take care of comparability between the two groups. The same data points will be compared after three and six months of consuming *chapattis*. Within six months, it is expected that serum retinol will be significantly increased in the fortified group compared to the unfortified group. We expect that the TfR will be decreased within six months since there will be fewer binding sites available.

Outcome measures including retinol, ferritin and TfR will be compared both within and between groups from start to the end of the trial. Change in nutritional status reflected by z-scores for WA, WH and HA, although not outcome measures, will also be investigated. Means of continuous variables, if normally distributed, will be compared by Student's t test. If the data of continuous variables do not conform to a Gaussian distribution, non-parametric tests including Mann-Whitney test will be used. Difference in categorical variables will be assessed by chi-square test. The confounding will be controlled by multiple regression analyses. An analysis of covariance will be performed for comparing the final levels of the outcome variables making allowances for any difference between the initial or 3-month levels.

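### The protocol describes the outcome as a before-after change, a 6-month level and an adjusted final level, and never says which comparison decides; the baseline-adjusted 6-month level should be named

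*Protocol*

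**What the plan says.** Four places in the protocol bear on this.

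- **Project Summary:** "status will be assessed by determining changes in serum concentrations of retinol, ferritin, transferrin receptor (TfR) and hemoglobin before and after intervention". This covers both arms, and change is not called primary there.
- **Specific Aims:** "Primarily, on their vitamin A status reflected in serum retinol concentration at 6 months". Ferritin, TfR and hemoglobin at 6 months come second.
- **Sample Size Estimation:** means and SDs before and after fortification are taken from two external studies and put into a formula for two independent groups: "Where, SD is the standard deviation and WD is the worthwhile difference between the means". The results are 83 per group for retinol and 87 for ferritin. Then "the calculated sample size has been doubled to 175 in each group to account for cluster and dropout effects". No correlation, SD of change, ICC or dropout rate is given.
- **Data Analysis:** the markers are compared at 3 and 6 months, and also within and between groups from start to end, by t test or Mann-Whitney test. Multiple regression is to deal with confounding. Finally, "An analysis of covariance will be performed for comparing the final levels of the outcome variables", with allowance for differences at either the initial or the 3-month measurement. No analysis is ranked above the others.

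**The concern.** Change from baseline, the unadjusted 6-month level and the baseline-adjusted 6-month level are three different variables with three different variances. If the deciding one is not fixed, it can be chosen after the results are seen, and one of the choices can cost precision. The sample size was computed for only one of them.

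The covariate is a separate weakness. The 3-month sample is drawn after three months of feeding, and the Project Summary says its purpose is to find the onset of a detectable change. It is therefore partly a result of treatment. An analysis that allows for it answers a narrower question than the one in the Specific Aims.

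**Working it through.** **Inputs (Sample Size Estimation).** Retinol: 29.2, SD 10.2, before and 34.2, SD 9.5, after (µg/dL), difference 5.0. Ferritin: 18.01, SD 13.8, before and 25.2, SD 15.3, after (µg/L), difference 7.19. Significance level 5%, power 90%. Two-sided testing is assumed because it reproduces the stated figures; one-sided testing gives 67 and 71. The factor is (1.96 + 1.2816)² = 10.507.

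**Step 1: reproduce the stated figures.** n = 2 × SD² × 10.507 / difference², with SD² the mean of the two variances.

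- Retinol: SD² = (10.2² + 9.5²)/2 = 97.1; n = 2 × 97.1 × 10.507 / 25 = 81.6, so 82 (83 with the t distribution). Stated: 83.
- Ferritin: SD² = (13.8² + 15.3²)/2 = 212.3; n = 2 × 212.3 × 10.507 / 51.7 = 86.3, so 87. Stated: 87.

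The calculation therefore uses SDs of levels and matches the 6-month level in the Specific Aims.

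**Step 2: the alternatives.** With r the baseline-to-6-month correlation (assumed; the protocol gives none):

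- variance of change = s1² + s2² − 2 r s1 s2
- variance of the baseline-adjusted level = SD² × (1 − r²)
- power = Φ(difference / √(2 × variance / n) − 1.96)

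Retinol at 83 per group, before clustering and dropout (unadjusted level: 90.5%):

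| r | SD of change | n per group for 90%, change | Power, change | Power, baseline-adjusted level |
|---|---|---|---|---|
| 0.2 | 12.47 | 131 | 73% | 91.5% |
| 0.3 | 11.67 | 115 | 79% | 93% |
| 0.4 | 10.81 | 99 | 85% | 95% |
| 0.5 | 9.87 | 82 | 90% | 96.5% |

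Ferritin at 87 per group behaves alike: change 73%, 78.5%, 84% and 90%; adjusted level 91%, 93%, 94% and 96%.

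**Step 3: break-even correlation before inflation.** The largest variance that keeps 90% power is n × difference² / (2 × 10.507).

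- Retinol, n = 83: 98.7, so r = (194.29 − 98.7)/193.8 = 0.49.
- Ferritin, n = 87: 214.0, so r = (424.53 − 214.0)/422.28 = 0.50.

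**Step 4: the planned 175 per group.** If all 175 counted as independent, change-score power would be 92% (retinol) and 90% (ferritin) even at r = 0. With 4 children per bari, the effective number is 175 × (1 − dropout)/(1 + 3 × ICC). With 10% dropout and the ICCs below, all assumed and taken as the same for change and level:

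| ICC | Effective n | Break-even r, retinol | Break-even r, ferritin |
|---|---|---|---|
| 0.05 | 137.0 | 0.16 | 0.21 |
| 0.10 | 121.2 | 0.26 | 0.30 |
| 0.20 | 98.4 | 0.40 | 0.43 |
| 0.30 | 82.9 | 0.49 | 0.52 |

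The threshold of about 0.5 applies to the enrolled sample only when clustering and dropout use up roughly the whole doubling.

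**Step 5: the 3-month covariate.** Let d3 and d6 be the true effects at 3 and 6 months, and b the slope of the 6-month value on the 3-month value. The adjusted comparison then estimates d6 − b × d3. With b positive, it understates d6 whenever the intervention has already raised the marker at 3 months. Baseline has no such effect, because it precedes randomised feeding.

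**The case against.** The strongest reply is that the protocol is already close to right. The Summary sentence is descriptive, and the next one calls the markers themselves the outcome measures. The word for primary stands only in the Specific Aims, and the sample size agrees with them. Data Analysis already plans an analysis of covariance of final levels that can allow for initial levels, and for that analysis the stated 90% is conservative. Ranking the methods is commonly left to a statistical analysis plan, which is not at hand.

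Most of this stands. A reader might infer that the primary outcome is a change score and that the trial misses 90% power unless the correlation reaches 0.5. The documents do not support that. Change is never called primary, no passage makes an unadjusted change the deciding test, and the 0.5 figure leaves out the doubling to 175. Nor does the mixed wording bias the comparison of means: randomisation makes the expected baseline difference zero, so change and level estimate the same between-arm effect.

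Two things remain that a later plan would have to correct in the protocol's own text. The Summary and the Aims describe the assessed quantity differently, and Data Analysis allows a covariate measured during the intervention.

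**Conclusion.** The point holds as an inconsistency of definition and a badly fixed covariate, not as a power failure. The between-arm analyses of means target one effect with unequal precision. In large samples the baseline-adjusted 6-month level is never less precise than the unadjusted level or the change, whatever the correlation. At the uninflated sizes, an unadjusted change would have 73% to 90% power for correlations of 0.2 to 0.5, against 91% to 96.5% for the adjusted level. Whether 175 per group would fall short for a change score depends on three quantities that the protocol does not state: correlation, ICC and dropout.

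The conservatism of the adjusted analysis rests on the protocol's averaged variance. If the ferritin SD of 15.3 from after fortification is used alone, the adjusted comparison needs 96 per group at r = 0, 92 at 0.2 and 87 at 0.3. This affects only a secondary marker. Overall this is a worthwhile improvement at no cost, not a flaw that threatens the trial.

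**What to change.** - **Project Summary, Specific Aims and Data Analysis:** name one deciding analysis for each marker, with retinol primary: the between-arm comparison of the 6-month serum concentration, with the baseline value of the same marker as covariate.
- **Data Analysis:** remove the 3-month value as a possible covariate in that analysis. Label changes from baseline and within-group comparisons as descriptive.
- **Sample Size Estimation:** state that the 90% refers to the 6-month level, and that adjusting for baseline can only improve on it under the same SD.

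Baseline, 3-month and 6-month samples are already scheduled for every child. The cost is a few sentences, with no change in sample size, visits or assays.

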## DESCRIPTION OF THE RESEARCH PROJECT

### Hypothesis to be tested:

Concisely list in order, in the space provided, the hypothesis to be tested and the Specific Aims of the proposed study. Provide the scientific basis of the hypothesis, critically examining the observations leading to the formulation of the hypothesis.

Consumption of *chapattis* made of wheat flour fortified with vitamin A and iron, in addition to the usual diet, will improve vitamin A and iron status of school aged children.

### Specific Aims:

Describe the specific aims of the proposed study. State the specific parameters, biological functions/ rates/ processes that will be assessed by specific methods (TYPE WITHIN LIMITS).

The aim of the study is to evaluate whether an impact of consuming *chapatti* made from vitamin A and iron fortified wheat flour by the school aged children can be demonstrated

1. Primarily, on their vitamin A status reflected in serum retinol concentration at 6 months
2. Secondly, on iron status reflected in serum ferritin, TfR and hemoglobin concentration at 6 months

## Background of the Project including Preliminary Observations

---

Describe the relevant background of the proposed study. Discuss the previous related works on the subject by citing specific references. Describe logically how the present hypothesis is supported by the relevant background observations including any preliminary results that may be available. Critically analyze available knowledge in the field of the proposed study and discuss the questions and gaps in the knowledge that need to be fulfilled to achieve the proposed goals. Provide scientific validity of the hypothesis on the basis of background information. If there is no sufficient information on the subject, indicate the need to develop new knowledge. Also include the **significance and rationale** of the proposed work by specifically discussing how these accomplishments will bring benefit to human health in relation to biomedical, social, and environmental perspectives. (DO NOT EXCEED 5 PAGES, USE CONTINUATION SHEETS).

---

### Background:

Other than iodine deficiency which poses risk to more than a billion people worldwide, lack of vitamin A and iron and consequences of their deficiencies are the two most recognized global public health problems (1). In addition to its effects on xerophthalmia, adequate vitamin A nutrition reduce upto a quarter to one-third of infection related childhood mortality (2,3,4,5). When given along with iron, vitamin A improves iron metabolism in anemic persons (6,7). The consequences of iron deficiency anemia include reduced physical capacity, impaired cognitive function and brain metabolism and reduced immunocompetence (1).

